6.3 Completion Status

Subjects will continue to receive study agent(s) until radiologic disease progression or unacceptable toxicity. Subjects unable to tolerate sorafenib may continue to receive mapatumumab/placebo every 21 days until radiologic disease progression. Subjects unable to tolerate mapatumumab/placebo may continue to receive sorafenib until radiologic disease progression. All subjects will have an End of Treatment visit at least 30 days after the last dose of sorafenib and/or mapatumumab/placebo, whichever is later. After discontinuation of treatment, subjects will continue to be followed for radiologic disease assessments every 6 weeks, starting 6 weeks after the previous disease assessment while on treatment, until documented radiologic disease progression (if not previously documented) and then every 3 months thereafter for survival until at least 90% of the subjects have met the survival endpoint. After discontinuation of study treatment, all subjects will return 1 day after cycle completion (approximately Day 22) and at least 30 days after the last dose of sorafenib and/or mapatumumab/placebo.

Completion will be summarized with respect to completion of the planned course of treatment, completion of required short-term follow-up and completion of required long-term follow-up. Completion of the planned course of treatment will be satisfied by subjects who are treated until radiologic disease progression. Completion of short-term follow-up will be satisfied by subjects who are followed through at least 30 days after the final dose (of any study agent) for scheduled safety assessments (or a pending disease assessment visit to confirm disease response if required), regardless of the reason for treatment discontinuation. Completion of long-term follow-up will be satisfied by those subjects who are followed for overall survival (OS). Completion of the study is defined as completing study treatment, completing short-term follow-up and completing long-term follow-up. Subjects still being followed at the time of any analysis will be counted as "ongoing".

6.4 Demographics and other Baseline Characteristics

Summary information related to medical history, sex, age, race, baseline disease state, and previous therapies will be presented. In general, counts and percentages will be presented for categorical data and mean, median, standard deviation, minimum, and maximum will be presented for continuous data.

6.5 Concomitant Medications

Concomitant medications will be coded according to drug name as defined in the World Health Organization (WHO) Drug Dictionary, classified according to the Anatomical Therapeutic Chemical (ATC) classification system and presented in tables and listings.

7 Efficacy Analyses

Efficacy analyses will be based on the BICR assessment. Evaluation of efficacy endpoints based on investigator data will be provided by applying modified Response Evaluation Criteria in Solid Tumors for hepatocellular carcinoma (mRECIST for HCC) (Lencioni, 2010 and Llovet, 2008) to investigator assessed tumor measurements. In addition, investigator reported objective response and disease control rates will be summarized with the caveat that these may differ from the application of mRECIST for HCC to the investigator assessed tumor measurements. Investigator reported disease progression dates will be presented in listings but not analyzed using time to event analysis techniques. Instead these analyses will be performed on time to progression (TTP) and progression free survival (PFS) dates resulting from application of mRECIST for HCC to investigator assessed tumor measurements along with the censoring guidelines and missing data rules described in this Analytical Plan.

7.1 Primary Efficacy Endpoint Analyses

7.1.1 Primary Efficacy Endpoint(s)

The primary endpoint is TTP defined as the time from randomization to radiologic disease progression based on BICR assessments of imaging scans using mRECIST for HCC (Llovet, et al, 2008 and Thomas, et al, 2010).

7.1.2 Primary Efficacy Analyses

The primary analysis will be an estimate of median TTP in each arm using Kaplan Meier methods, reported with 95% confidence intervals, along with testing the hazard ratio for TTP at a 1-sided significance level of 0.10 with a Cox proportional hazards model controlling for the factors stratifying the randomization as covariates.

7.1.3 Additional Analyses of Time to Progression

While the primary analysis of TTP is based on the BICR determination of radiologic disease progression, additional analysis will be performed.

- An analysis of TTP as determined by the BICR censoring subjects at the date of the last complete disease assessment performed prior to any protocol prohibited medications/therapy as specified in Section 5.3 of the protocol (eg, cytotoxic chemotherapy, hormonal therapy, biological therapy, immunotherapy or locoregional therapy).
- An analysis of TTP based on application of mRECIST for HCC to investigator assessed tumor measurements. In this analysis all subjects will be censored for TTP at the date of the last complete disease assessment performed prior to any protocol prohibited locoregional therapy.

- An analysis of TTP based on application of mRECIST for HCC to investigator assessed tumor measurements censoring subjects at the date of the last complete disease assessment performed prior to any protocol prohibited medications/therapy (eg, cytotoxic chemotherapy, hormonal therapy, biological therapy, immunotherapy or locoregional therapy).

7.1.4 Adjustment for Covariates

Adjustment for covariates including the stratification factors BCLC advanced stage C vs. BCLC intermediate stage B and ECOG performance status (0 vs. 1, 2) is planned for the primary analysis as well as the analyses described in Section 7.1.3.

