Sorafenib is the standard of care for treatment of patients with advanced hepatocellular carcinoma. Sorafenib is a multikinase inhibitor that targets the Raf/mitogen-activated protein kinase/extracellular signal-regulated kinase signaling pathway, blocks tumor angiogenesis and induces apoptosis (Panka et al, 2006; Rahmani et al, 2005; Yu et al, 2005; Wilhelm et al, 2004). Sorafenib was approved by the European Medicines Agency and the Food and Drug Administration in 2007 for treatment of patients with hepatocellular carcinoma based on the demonstration of improved overall survival in the 602 patient randomized, placebo-controlled, Phase 3 “Sorafenib Hepatocellular Carcinoma Assessment Randomized Protocol” (SHARP) trial. Approximately half the 602 patients had either hepatitis C virus or hepatitis B virus as underlying etiology and 26% had alcohol-related cirrhosis. The median overall survival was 10.7 months for patients in the sorafenib arm compared with 7.0 months for patients in the placebo arm (hazard ratio in the sorafenib group, 0.69 95% confidence interval, 0.55 to 0.87; $p < 0.001$). The median time to radiologic progression was 5.5 months in the sorafenib arm, compared with 2.8 months in the placebo arm ($p < 0.0001$) (Llovet et al, 2008). Seven patients in the sorafenib group (2%) and 2 patients in the placebo group (1%) had a PR; no patients had a CR.

A 2nd randomized, placebo-controlled Phase 3 trial was conducted in the Asia-Pacific region (Cheng et al, 2009). The 226 patients randomly assigned to sorafenib or placebo in this trial appeared to have more advanced disease than those in the SHARP trial, with a higher frequency of extrahepatic spread, poorer ECOG PS, and higher levels of AFP, but still showed a benefit from treatment with sorafenib. The majority (73%) had hepatitis B virus as an underlying etiology. The median overall survival was 6.5 months for patients in the sorafenib arm, compared with 4.2 months in the placebo group (hazard ratio, 0.68, 95% confidence interval, 0.50-0.93; $p = 0.014$). The median time to progression was 2.8 months in the sorafenib group, compared with 1.4 months in the placebo group (hazard ratio, 0.57, 95% confidence interval 0.42-0.79; $p = 0.0005$).

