6.1 Screening Procedures

The nature of this study and the potential risks and benefits associated with participation in the study will be explained to all potential study subjects. Written informed consent (including consent for the use and disclosure of research-related health information) must be obtained before any screening procedures are performed that are not considered standard of care.

All of the following assessments must be performed within 28 days prior to enrollment:

- Obtain written informed consent for participation in the study.
- Obtain informed consent for participation in the optional biomarker sub-study.
 - If consented, obtain tissue block/slides or cell pellet from diagnostic histologic/ cytologic sample.
- Record demographics.
- Obtain medical history, to include history of all treatments used to treat the current cancer and all prior cancer treatments.
- Perform baseline complete physical examination including body weight and height.
- Assess vital signs (blood pressure, heart rate, respiratory rate and temperature).
- Evaluate performance status (ECOG scale; see [Appendix 3](#)).

- Draw blood for laboratory tests (see [Appendix 7](#)): complete blood count with differential, chemistry, hepatitis B surface antigen, Hepatitis B virus DNA, hepatitis C antibody and testing for serum pregnancy (all females with an intact uterus [unless amenorrheic for the previous 24 months] regardless of age).
- Obtain radiologic disease and AFP assessments. The method of disease assessment, as per mRECIST for HCC (see [Appendix 5](#)), will be consistent throughout the study.
- Obtain electrocardiogram.
- Record medications used within 28 days before enrollment.
- Confirm that subject meets all inclusion/exclusion criteria.

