2.2 Secondary Study Objectives

The secondary objectives of this study are:

- To evaluate the safety of mapatumumab in combination with sorafenib in subjects with advanced hepatocellular carcinoma.
- To determine serum mapatumumab concentrations.

3 Study Administrative Structure

Human Genome Sciences (HGS) is the sponsor of this study. Data collected for this study will be recorded electronically on case report forms (eCRFs) provided or approved by the sponsor.

Sites will enter subject data directly into the eCRF system which will automatically generate queries resulting from computer checks embedded into the system, so as to ensure accuracy, quality, consistency, and completeness of the database. Manual queries resulting from review by monitors, medical coders, and other Data Management staff are also generated from within the electronic data capture system, where they are tracked. Sites resolve the queries and correct the entered data when necessary. Every change to data is captured in the electronic data capture system audit trail.

HGS will have discretion to lock the database when 90% of all randomized and treated subjects have been followed to radiologic disease progression, or when all subjects have been followed for at least 12 months at which point blinded review of the remaining data will facilitate a decision on whether to lock the database or wait for remaining events.

4 Study Design

In addition to receiving sorafenib, subjects will be randomly assigned to 1 of 2 treatment groups in a 1:1 ratio: 30 mg/kg mapatumumab or placebo. Approximately 100 subjects with advanced hepatocellular carcinoma will be randomized. Randomization will be stratified according to Barcelona Clinic Liver Cancer (BCLC) advanced stage C vs. BCLC intermediate stage B and Eastern Cooperative Oncology Group (ECOG) performance status (0 vs. 1, 2).

Radiologic eligibility must be confirmed by a blinded independent central review (BICR) prior to randomization. Subjects will receive treatment every 21 days (ie, a cycle) as outlined below:

Arm A: Sorafenib 400 mg orally twice daily continuously in each cycle + placebo intravenously on Day 1 of each cycle

Arm B: Sorafenib 400 mg orally twice daily continuously in each cycle + mapatumumab (30 mg/kg) intravenously on Day 1 of each cycle

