5.1 Determination of Sample Size

A total of approximately 100 subjects will be randomly assigned to 1 of 2 arms and treated with either sorafenib + placebo or the 2-agent combination of sorafenib + mapatumumab 30 mg/kg in a 1:1 ratio. A sample size of 50 subjects randomized and treated in each group is sufficient to estimate the median time to progression (TTP) with a precision of approximately -1.9 months to +2.6 months relative to the observed median. In addition, a sample size of 50 patients per arm will provide 80% power to detect an improvement in TTP from 5.5 to 8.9 months with at a one-sided significance level of 0.10.

6 Study Subjects

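### The primary Cox model for TTP is valid, but it makes no use of baseline AFP, which is already collected, and SAP 7.1.4 leaves the covariate list open

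*SAP*

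**What the plan says.** SAP 7.1.2 makes the primary test "testing the hazard ratio for TTP at a 1-sided significance level of 0.10 with a Cox proportional hazards model". The adjustment in that model is for the randomization strata. Protocol 9.3.2 and the synopsis say the same. SAP 7.1.4 covers the primary analysis and the additional TTP analyses of 7.1.3, and plans "Adjustment for covariates including the stratification factors BCLC advanced stage C vs. BCLC intermediate stage B and ECOG performance status". ECOG enters as 0 against 1 or 2. No other covariate is named. SAP 7.2.3 uses the same form of words for PFS and OS.

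AFP is a required screening item: Protocol 6.1 has "Obtain radiologic disease and AFP assessments". Protocol 1.5 describes the population of the second phase 3 sorafenib trial as appearing more advanced, "with a higher frequency of extrahepatic spread, poorer ECOG PS, and higher levels of AFP". Median TTP on sorafenib was 2.8 months there, against 5.5 months in the first trial. The SAP uses AFP only in 7.6.1, an exploratory AFP-response analysis in subjects with baseline AFP of at least 400 µg/L. AFP is not a covariate, a stratification factor or a listed subgroup.

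On size, SAP 5.1 states that "a sample size of 50 patients per arm will provide 80% power to detect an improvement in TTP from 5.5 to 8.9 months" at one-sided 0.10. SAP section 4 adds: "Approximately 100 subjects with advanced hepatocellular carcinoma will be randomized".

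**The concern.** Two separate things are at issue.

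The first is efficiency. In a Cox model, leaving out a covariate that predicts the outcome pulls the treatment hazard ratio toward 1 and costs power, even when randomization balances that covariate. The protocol's background puts AFP next to ECOG as a marker of advanced disease. ECOG is in the model and AFP is not, although every subject should have a value. With about 100 subjects and a planned power of 80%, a few points are worth having.

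The second is pre-specification. SAP 7.1.2 implies exactly two covariates, while *including* in 7.1.4 allows more. A covariate added after unblinding would depart from 7.1.2 but could be defended from 7.1.4. With one-sided alpha of 0.10 and fewer than 100 events, that choice could change the conclusion.

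**Working it through.** **The plan's own figure.** Under exponential times the design hazard ratio is 5.5/8.9 = 0.618, with ln = −0.481. By Schoenfeld's formula, events = 4(1.282 + 0.842)²/0.481² ≈ 78. Power at 78 events is Φ(0.481·√78/2 − 1.282) = Φ(0.844) = 80.1%, so the stated 80% reproduces. The stated precision of −1.9/+2.6 months agrees: 2.6/1.9 = 1.368, ln = 0.314, SE = 0.314/1.96 = 0.160, so 1/0.160² ≈ 39 events per arm, or 78 in total. The 78 is inferred; no event target is stated. SAP section 3 allows lock at 90% progressed, and about 90 events would give 84.2%.

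**Effect of adding AFP.** The documents give no AFP effect on TTP, so the inputs below are assumptions: n = 100, about 78 events, hazard ratio 1.4 each for BCLC and ECOG, 80% stage C, 50% ECOG 1–2. BCLC and ECOG are in both models.

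*Continuous log AFP, independent of BCLC and ECOG, treatment hazard ratio 0.618 conditional on AFP (2,500 simulated trials each):*

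| AFP hazard ratio per SD | Two-factor model | With log AFP | Gain (points) |
|---|---|---|---|
| 1.0 | 80.9% | 81.0% | 0.1 |
| 1.2 | 79.7% | 80.4% | 0.7 |
| 1.4 | 76.8% | 79.9% | 3.1 |
| 1.65 | 73.4% | 80.8% | 7.4 |

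A separate simulation, also with BCLC and ECOG in both models at 78 events, gave lower power throughout but similar gains: 77% to 76% with no AFP effect, 76% to 76% at 1.2, 73% to 77% at 1.4 and 69% to 76% at 1.65. The differences are more reliable than the absolute levels.

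*AFP as high versus low, 40% high (3,000 to 5,000 trials each).* In the scaled columns, the treatment effect is enlarged until the two-factor model has about 80% power:

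| AFP hazard ratio, high vs low | Treatment HR 0.618: without → with | Scaled to about 80%: without → with |
|---|---|---|
| 1.0 | 78.4% → 78.2% | – |
| 1.25 | 77.0% → 77.5% | 80.4% → 80.5% |
| 1.5 | 76.2% → 77.4% | 79.9% → 81.0% |
| 2.0 | 73.5% → 77.5% | 79.8% → 82.9% |

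The two scales can be linked. With 40% high, the SD of the indicator is √(0.4 × 0.6) = 0.49. A hazard ratio per SD of 1.4 then corresponds to exp(0.336/0.49) ≈ 2.0 high versus low, and 1.65 to exp(0.501/0.49) ≈ 2.8.

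At about 90 events with the treatment hazard ratio at 0.618, the gains are similar: 81.6% → 82.6% at 1.5 and 78.8% → 82.7% at 2.0.

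**Type I error.** Under no treatment effect with a high-versus-low AFP hazard ratio of 2.0, one-sided error was 11.1% without AFP and 10.7% with it (nominal 10%). The slight excess is common to both models.

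**Missing AFP.** If subjects without AFP are dropped, the gain can vanish. At a high-versus-low hazard ratio of 1.5, the two-factor model on all subjects has 76.8%. The AFP model has 76.1% with 5% missing and 74.8% with 10%. At 2.0 the two-factor figure is 74.8%, against 75.7% with 10% missing and 73.4% with 15%. With 10% missing and mean imputation that ignores arm and outcome, the gain survives: for continuous log AFP, 76.9% → 81.0% at 1.4 per SD and 72.8% → 80.1% at 1.65, with 80.6% → 80.4% when AFP has no effect.

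**The case against.** The strongest reply is that nothing here is an error. Adjusting for the stratification factors is a sound primary analysis, it is specified consistently in SAP 7.1.2 and Protocol 9.3.2, and its type I error is unaffected. That stands.

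A reader might infer from Protocol 1.5 that AFP explains the gap between 2.8 and 5.5 months. The documents do not support this. The passage compares two trials that also differed in extrahepatic spread, ECOG and region, and 73% of the second population had hepatitis B. It gives no patient-level effect of AFP, still less one beyond BCLC and ECOG. By the same argument one could propose extrahepatic spread or hepatitis status. AFP has the practical advantage that it is a single number required at screening, but that is a judgement.

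The size is also open to challenge. Holding 0.618 as the effect conditional on AFP lowers the two-factor power by construction, whereas SAP 5.1 frames the effect as a difference in medians without reference to AFP. Scaling the two-factor model to 80% cuts the gain to 1 to 3 points. This stands, and both versions should be reported.

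Finally, 7.1.2 can be read as already fixing the covariates, so that *including* is loose drafting. That is probably the intent, but the text of 7.1.4 does not say so.

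**Conclusion.** The point holds as an inexpensive improvement and a gap in pre-specification. The primary test is valid as planned.

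The gain from adding log baseline AFP is 0 to 1 point of power if AFP is weakly prognostic. It is about 3 to 7 points at an assumed hazard ratio per SD of 1.4 to 1.65 with the treatment hazard ratio at 0.618 conditional on AFP. It is about 1 to 3 points, at a high-versus-low hazard ratio of 1.5 to 2.0, when the two-factor model is scaled to 80%. If AFP is not prognostic the loss is negligible. All of this rests on assumed AFP effects and on about 78 events, which is inferred.

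Two stronger readings are tempting and neither is supported. One is that the trial is underpowered because AFP is missing from the model: the stated 80% reproduces, and the documents give no AFP effect from which to compute a shortfall. The other is that the change is free: it needs a functional form and a missing-value rule, it makes the hazard ratio conditional on AFP as well as on BCLC and ECOG, and complete-case deletion could turn the gain into a loss.

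**What to change.** Before unblinding:

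- In SAP 7.1.2 and 7.1.4, list the primary covariates as exactly BCLC stage, ECOG (0 vs 1, 2) and log-transformed baseline AFP. Remove *including*, and close the list in 7.2.3 as well.
- State one imputation rule for missing baseline AFP that is blind to arm and outcome, such as the overall mean of log AFP. Do not delete subjects. The baseline rule in SAP section 5 already falls back on the screening value.
- Keep the two-factor model as a named sensitivity analysis.
- Make the same change in Protocol 9.3.2 and the synopsis, so that protocol and SAP do not conflict.

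The cost is a few sentences in the SAP, a matching protocol edit and no new data. If the sponsor prefers the two-factor model as primary, the minimum is to close the list and pre-specify the AFP-adjusted model as the sensitivity analysis. If treatment-level results have already been seen, AFP adjustment should be reported only as a post hoc sensitivity analysis.

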7.1.5 Subgroup Analyses

Subgroup analyses may be performed on the stratification factors BCLC advanced stage C vs. BCLC intermediate stage B and ECOG performance status (0 vs. 1, 2). Subgroup analyses may also be performed on laboratory parameters testing for the hepatitis B surface antigen and the hepatitis C surface antibody (positive for the hepatitis B surface antigen vs. not, positive for the hepatitis C surface antibody vs. not).

7.2 Major Secondary Efficacy Endpoint Analyses

7.2.1 Major Secondary Efficacy Endpoints

Secondary efficacy endpoints include overall survival, progression free survival, objective response, disease control, time to response (for responders), and duration of response (for responders) as defined below:

- Overall survival (OS): time from randomization to death from any cause.
- Progression free survival (PFS): time from randomization to radiologic disease progression or death from any cause.
- Objective response: CR+PR according to mRECIST for HCC.
- Disease control: CR+PR+SD according to mRECIST for HCC.
- Time to response: time from randomization to 1st PR or CR in responders only.
- Duration of response: time from 1st PR or CR to radiologic disease progression; in responders only.

such that CR is complete response, PR is partial response and SD is stable disease.

All secondary endpoints will be based on BICR assessments of imaging scans. Additional analyses based on application of mRECIST for HCC to investigator assessed tumor measurements, or investigator determination of disease response will be performed. For

the purposes of establishing SD based on BICR or application of mRECIST for HCC to investigator assessed tumor measurements, at least 6 weeks from the baseline measurement must elapse without progressive disease (PD) in order to assign a best overall response of SD. Confirmation of PR and CR will occur no fewer than 4 weeks after initial documentation of PR or CR. If PR or CR that is pending confirmation is designated at an assessment followed by 1 or more non-evaluable assessments or assessments of SD, response may be confirmed thereafter.

7.2.2 Major Secondary Efficacy Analyses

Secondary analyses include estimates, using Kaplan Meier methods, of median PFS and median OS along with associated logrank testing. The hazard ratio will also be estimated for PFS and OS using Cox proportional hazard modeling adjusting for factors stratifying the randomization as covariates. In addition, estimates of overall response rate (CR+PR) and disease control rate (CR+PR+SD) will be reported with 95% confidence intervals and an estimate of the difference in response rates and disease control rates between groups will be reported and tested for significance with a Pearson chi-square test (or Fisher's exact test, as appropriate). The analysis of PFS as determined by the BICR described in this section will be repeated, but with PFS based on application of mRECIST for HCC to investigator assessed tumor measurements. Analyses of TTP as described in Section 7.1.3 will be repeated for PFS. In addition, the analyses of objective response, disease control, time to response and duration of response will be repeated with 2 analyses: 1) with endpoints based on application of mRECIST for HCC to investigator assessed tumor measurements and 2) with endpoints as provided directly by the investigator.

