4.4 Treatment Assignment

Subjects that meet the eligibility criteria will be randomly assigned treatment by a central interactive web response system (IWRS) in a 1:1 ratio to 1 of 2 treatment arms (Arm A: sorafenib + placebo or Arm B: sorafenib + mapatumumab 30 mg/kg). The randomization will be stratified according to BCLC advanced stage C vs. BCLC intermediate stage B and ECOG performance status (0 vs. 1, 2) as defined in Appendices 2 and 3 of the protocol, respectively.

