4.6 Interim Analysis

This study has no interim analysis planned.

5 General Statistical Considerations

Statistical analyses performed on the efficacy data will be applied to a modified intention-to-treat (MITT) population unless stated otherwise. This population is defined as the set of all randomized subjects who receive at least part of 1 dose of study agent (mapatumumab/placebo and/or sorafenib) with subjects analyzed according to the groups to which they are randomized, regardless of the treatment they subsequently receive. Additional analyses may be performed on the as-treated population, defined as the set of subjects receiving at least part of 1 dose of study agent analyzed according to the treatment that they actually receive. All analyses performed on safety, subject disposition, exposure and completion status will be applied to the as-treated population. Analyses performed on demographics and concomitant medications data will be applied to the MITT population.

Assessments will be referred to by day of cycle beginning with Cycle 1/Day 1. This will allow data from subjects with small fluctuations in cycle length, or dosing delays to be reported in a consistent fashion. Cycle 1/Day 1 (predose) will typically be the baseline assessment unless data are missing, in which case screening data closest to the Cycle 1/Day 1 assessment will be used. In the instance a subject discontinues all treatment, or discontinues mapatumumab/placebo, but remains on sorafenib treatment, an off-treatment distinction will be made when referencing disease assessments.

Categorical data analyses using the Pearson chi-square test will substitute Fisher's exact test if > 20% of expected contingency table cell counts are < 5.

Analyses will be performed using the SAS SystemTM, WinNonlin Enterprise EditionTM, StatXactTM, and the R statistical package.

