7.2.3 Adjustment for Covariates

Adjustment for covariates including the stratification factors BCLC advanced stage C vs. BCLC intermediate stage B and ECOG performance status (0 vs. 1, 2) is planned for secondary endpoints PFS and OS in Cox proportional hazard modeling and logrank testing.

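### Disease control is tested without the BCLC and ECOG strata that TTP, PFS and OS are adjusted for; the test is valid, and noticeably conservative only if both strata are fairly strongly prognostic

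*SAP*

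**What the plan says.** SAP 4.4: "The randomization will be stratified according to BCLC advanced stage C vs. BCLC intermediate stage B and ECOG performance status (0 vs. 1, 2". That makes four strata.

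The time-to-event endpoints use those factors. SAP 7.1.2 tests TTP in a Cox model "controlling for the factors stratifying the randomization as covariates", and SAP 7.1.4 says that adjustment "is planned for the primary analysis as well as the analyses described in Section 7.1.3". For the secondary endpoints, SAP 7.2.3 says that adjustment "is planned for secondary endpoints PFS and OS in Cox proportional hazard modeling and logrank testing" and names no other endpoint.

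Disease control (CR+PR+SD) is compared in SAP 7.2.2 as follows: "disease control rates between groups will be reported and tested for significance with a Pearson chi-square test (or Fisher's exact test, as appropriate". Protocol 9.3.4 plans the same. SAP Section 5 gives the switching rule: the Pearson test "will substitute Fisher's exact test if > 20% of expected contingency table cell counts are < 5". SAP 7.2.2 also repeats the disease-control analysis twice, once with mRECIST applied to the investigator's measurements and once with the investigator's own determination. SAP 7.2.4 permits optional subgroup analyses by the same factors. Neither document provides a stratified or adjusted test of disease control.

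**The concern.** Disease control is read from the same scans, by the same central review, as progression, yet it is compared on a different basis. Stratified randomization makes the arms more alike on BCLC stage and ECOG group than chance would. A test that ignores the strata uses a variance that takes no credit for this balance. If the factors predict disease control strongly enough, the test rejects less often than its nominal level, and some power is lost in a trial of about 50 per arm. What is at stake is the efficiency and consistency of one secondary comparison; the primary analysis is untouched.

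**Working it through.** **The plan's own figure.** SAP 5.1 claims "80% power to detect an improvement in TTP from 5.5 to 8.9 months" at one-sided 0.10 with 50 per arm. HR = 5.5/8.9 = 0.618. Schoenfeld events = 4(1.2816 + 0.8416)²/(ln 0.618)² = 18.03/0.2317 = 77.8, so 78, which gives 80.1% power. The figure reproduces. There is no corresponding figure for disease control, and neither an alpha nor a sidedness is stated for it, so two-sided 0.05 and one-sided 0.10 were both examined.

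**Inputs from the documents.** N = 100, 1:1, four strata. Non-evaluable subjects stay in the denominator (SAP 7.3). For SD, "at least 6 weeks from the baseline measurement must elapse without progressive disease (PD) in order to assign a best overall response of SD" (SAP 7.2.1). Sorafenib median TTP is 5.5 or 2.8 months in the two cited trials (Protocol 1.5). Taking 6 weeks as 1.38 months and assuming exponential TTP:

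- 0.5^(1.38/5.5) = 0.84
- 0.5^(1.38/2.8) = 0.71
- the second rate with an assumed 10% non-evaluable: 0.71 × 0.9 = 0.64

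**Assumptions not in the documents.** Odds ratio (OR) per stratification factor of 1, 1.5, 2 or 3; stratum mix 50/50 on both factors, or 80% stage C with ECOG 50/50; permuted blocks of 4; constant treatment log-odds.

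**Hand check of the direction.** With arms balanced within strata and no treatment effect, the variance of the unstratified Pearson z is about mean[p_s(1−p_s)] / [p̄(1−p̄)], where p_s is the rate in stratum s. Take p̄ = 0.64 (denominator 0.2304) and even strata.

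- OR 2 on both factors: stratum rates 0.479, 0.648, 0.648, 0.786; mean p_s(1−p_s) = 0.2185; ratio 0.948; size 2[1−Φ(1.96/√0.948)] = 4.4%.
- OR 3 on both factors: rates 0.391, 0.658, 0.658, 0.852; mean 0.2035; ratio 0.883; size 3.7%.

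Simulated sizes are slightly higher, because incomplete blocks leave some imbalance and the test is discrete.

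**Simulated size, nominal two-sided 5%, control rates 64% and 71%.** Pearson: 4.6–4.8% at OR 2 and 3.9–4.2% at OR 3. CMH: 4.9–5.1%. Simulation error is about √(0.05 × 0.95/40,000) = 0.1 point.

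**Simulated power, two-sided 0.05, even strata, Pearson → CMH (100,000 trials each).**

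| OR per factor, both factors | 64% vs 84% | 71% vs 90% |
|---|---|---|
| 1 | 63.9 → 63.3 | 69.5 → 68.7 |
| 1.5 | 63.9 → 63.9 | 69.5 → 69.2 |
| 2 | 64.3 → 65.4 | 69.7 → 70.1 |
| 3 | 65.0 → 68.0 | 69.9 → 72.0 |

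For these two pairs of rates and both stratum mixes, the two-sided gain is about 0.2–1 point at OR 2 and 1–3 points at OR 3. If only one factor is prognostic, at OR 2, the change is about −0.4 to +0.3 points. At one-sided 0.10, OR 3 on both factors gains 0.7–1.3 points. Over seven pairs of rates (control 50–84%), both mixes and both alphas, the change is −1.1 to +0.1 (OR 1), −0.7 to +0.5 (OR 1.5), −0.2 to +1.3 (OR 2) and +0.3 to +3.8 (OR 3).

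**Separating out Fisher's test.** In a 2×2 table one small cell is 25% of the cells, so any expected count below 5 triggers the switch. With 50 per arm that means a pooled disease-control rate above 90%. At 84% vs 97% the pooled rate is 90.5%, and Fisher's test is used in 65% of trials. Moving from the planned test to Pearson there changes power from 54.7% to 63.7% (OR 2). That is the cost of Fisher's test and is not counted here; the strata add only 0.8–0.9 points at OR 2 and 1.5–1.9 at OR 3.

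**The case against.** The strongest reply is that this is a preference. An unadjusted risk difference with a chi-square test is a legitimate prespecified choice for a phase 2 secondary endpoint. SAP 7.1.4 and 7.2.3 show that adjustment was considered and confined to the time-to-event endpoints. Nothing in the documents says that BCLC stage or ECOG group predicts disease control, and if they do not, CMH loses a little power. All of this stands, and it limits the point to a minor improvement.

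It also stands that conservatism needs more than some prognostic value in the strata. Across all the null scenarios the size at OR 2 runs from 4.6% to 5.3%, on both sides of nominal; a consistent shortfall appears only at OR 3 (3.9–4.5%).

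A reader might infer that an analysis ignoring the randomization strata is invalid, inflates type I error, or contradicts the rest of the SAP. The documents do not support this. The passages cover different endpoints, and the omission can only make the test more cautious. A reader might also extend the point to objective response, which is tested in the same sentence. The only response rate in the documents is 2% PR on sorafenib (Protocol 1.5). At that rate the strata make no difference, and any conservatism comes from Fisher's test. That rate may not carry over to mRECIST, which takes account of vascularity, so nothing is claimed for objective response.

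The 6-week anchor is rough: the SD clock starts at the baseline measurement, whereas TTP starts at randomization. The overall pattern holds over control rates of 50–84%.

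**Conclusion.** The point holds as a minor one. Disease control is the one comparison examined here that omits the randomization strata, although its scans also feed stratum-adjusted analyses. The planned test remains valid. A noticeable cost requires both factors to have an odds ratio of about 2 or more: about 0.2–1 power point at 2, and 1–3 points at 3. Below that, or with a single prognostic factor at 2, the two tests are interchangeable within about 1 point.

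The odds ratios, stratum mixes, block size and disease-control rates are all assumptions. The nearest thing to evidence in the documents is the contrast between the two cited sorafenib trials. Six-week no-progression rates of 84% and 71% give an odds ratio of (0.84/0.16)/(0.71/0.29) = 2.1. That contrast mixes every difference between two trial populations, so it does not establish an effect of either factor and gives no support for per-factor effects well above 2.

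**What to change.** In SAP 7.2.2 and 7.2.3 and Protocol 9.3.4:

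- Test disease control with a Cochran-Mantel-Haenszel test stratified by BCLC stage (C vs B) and ECOG group (0 vs 1–2).
- Use its exact version when the small-expected-count rule of SAP Section 5 applies, and say which table the rule refers to. Keeping it on the pooled 2×2 table preserves the present trigger.
- Report the Mantel-Haenszel risk difference with a 95% CI. SAP 7.2.2 promises intervals for the rates but does not state one for the difference.
- Apply the same method to the two repeated investigator-based disease-control analyses.
- Keep the unadjusted rates as descriptive output.

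This should be specified before unblinding. Amendment 3 records that at least 90% of subjects had met the survival endpoint and allows unblinded extended treatment, so treatment results may already be known. In that case the planned test should stay, with the stratified one reported as a labelled supplementary analysis.

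The cost is wording and one procedure option. No new data are needed, since the strata are recorded at randomization. The downside is at most about 1.1 power points if the strata are not prognostic.
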